Sample Size Calculation: This is a randomized, double-blinded, placebo-controlled clinical trial that aims to evaluate the effects of liraglutide on motor and non-motor symptoms in patients diagnosed with PD. The primary outcome of this study will be the difference in MDRS-2 scores at baseline and follow-up (52 weeks after titration) between the active and placebo control group. The power analysis was performed utilizing data reported in a previous study using a similar GLP-1 agonist (**Table 1**). While score changes associated with active medication were not compared to a placebo group but to a cohort of patients treated with “conventional PD medication”, this data represent the closest approximation available for power analysis and sample size calculation.

With a total of 57 patients (38 in the drug group and 19 in the placebo group), the study will have an 82.7% chance of rejecting the null hypothesis of equal means, assuming an average critical difference of 5.1 points on the MDRS-2 and a standard deviation of 6.4 for the drug group and 5.3 for the placebo group with a significance level (alpha) of 0.050 using a two-sided two-sample unequal-variance t-test.

This sample allows for a 12% dropout of up to 6 subjects (e.g., if they are diagnosed with T2D during the course of the study) and still maintain 81.3% power with a total of 51 patients (i.e., 36 cases in the drug group and 15 cases in the placebo group). If the rate of drop out is higher than anticipated, the study will enroll and randomize additional subjects; subjects will be enrolled/randomized in multiples of 3 subjects in order to maintain the 2:1 randomization. The additional enrolled subjects will aim to maintain the power of the study. In total, up to 63 patients will be enrolled and randomized. No more than 42 patients, including drop outs, will be exposed to the drug during the trial.

Statistical Methods: The analysis populations for this study are defined as:

1. Full Analysis Set (FAS): all randomized subjects who receive at least one dose of study drug and have a baseline and at least one post-baseline efficacy score (MDRS-2 and MDS-UPDRS).
2. Per-Protocol (PP) population: a subset of the FAS population, excluding subjects with major deviations from the protocol that may substantially affect the results of the primary efficacy analysis.
3. Safety population: all randomized subjects who receive at least one dose of study drug.

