Descriptive statistics: The study population will be described using demographic, baseline, and subject characteristics. Descriptive statistics of demographic, baseline, and subject characteristics will be based on the Safety population. A detailed description of subject disposition will include:

- A summary of data on subject discontinuations including reason for withdrawal
- A summary of protocol violations and deviations

All screened subjects will be accounted for in the disposition summaries. The number and percentage of subjects included in each analysis population will be summarized.

Baseline and subject characteristics will include a summary of the following:

- Subject demographics
- Medical history including family history

- Physical examination findings
- Prior and concomitant medications/therapies
- HoMA-IR and QUICKI index at baseline
- MDRS-2 scores at baseline
- MDS-UPDRS scores at baseline
- Non-Motor Symptoms Scale (NMSS) scores at baseline
- PDQ-39 Quality of Life scale scores at baseline
- Delis-Kaplan Executive Function System (DKEFS), Geriatric Depression Scale, and Parkinson's Anxiety Scale scores at baseline

Inferential Statistics on Primary Efficacy Parameter(s): The primary analysis of efficacy endpoint (changes in UPDRS, NMSS, and MDRS-2 scores between baseline and Week 54) will be assessed using a two-sided, two-sample unequal-variance t-test to evaluate the differences in end points between the active and placebo cohorts. Multiple regression analysis will be used for comparisons of between-cohort differences in these outcomes over time. General linear models will be used to evaluate possible associations between baseline characteristics and the primary endpoints. Analysis of covariance (ANCOVA) will be used to evaluate possible effects of peripheral insulin sensitivity and treatment group (independent variables) on the primary end points (dependent variable). Hochberg's method for adjustment for multiple testing separately for the primary end points and secondary endpoints will also be used.

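### The plan contradicts itself on the primary success rule, and its 81.3% power after dropout is right only if MDRS-2 is tested alone or unadjusted; under Hochberg it is a ceiling over a floor of 66.0%

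*Combined protocol and SAP*

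**What the plan says.** Four statements in the combined protocol and SAP bear on what counts as a positive primary result.

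- **Sample Size Calculation.** MDRS-2 change is named as the primary outcome. Power is computed "with a significance level (alpha) of 0.050 using a two-sided two-sample unequal-variance t-test". The inputs are a difference of 5.1 points, an SD of 6.4 on drug and an SD of 5.3 on placebo. For 57 patients (38 drug, 19 placebo), "the study will have an 82.7% chance of rejecting the null hypothesis of equal means". After six losses, leaving 36 on drug and 15 on placebo, the trial would "still maintain 81.3% power with a total of 51 patients".
- **Endpoints.** Three primary outcomes are listed: MDS-UPDRS Part III, NMSS and MDRS-2.
- **Inferential Statistics on Primary Efficacy Parameter(s), first paragraph.** The primary endpoint is given as "changes in UPDRS, NMSS, and MDRS-2 scores between baseline and Week 54". The paragraph closes by saying that Hochberg's "method for adjustment for multiple testing separately for the primary end points and secondary endpoints will also be used".
- **Same section, last paragraph.** It says that the Type I error rate has not been adjusted for multiple primary or secondary comparisons, because the study is phase II.

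**The concern.** The power statement and the analysis section describe different success rules. The first has one endpoint and one threshold, 0.05. The second has three endpoints and, on one of its two statements, a step-up procedure in which the MDRS-2 threshold depends on the other two p-values. Nothing in the Sample Size Calculation allows for those two endpoints.

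Two things are at stake. First, the same MDRS-2 p-value, say 0.03, could be a success or a failure depending on which sentence is followed, and that choice could be made after the data are seen. Second, the six-patient dropout allowance is defended by the 81.3%. If Hochberg is the rule, that figure describes the most favourable case, and a missed MDRS-2 result could be read as stronger evidence against an effect than the sample supports.

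**Working it through.** **Inputs (all from Sample Size Calculation):** difference d = 5.1; SD 6.4 (drug) and 5.3 (placebo); n = 38/19 at full size and 36/15 after dropout; two-sided Welch t-test.

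**Formulas.** With v1 = 6.4²/n1 and v2 = 5.3²/n2:
- SE = √(v1 + v2)
- Satterthwaite df = (v1 + v2)² / [v1²/(n1−1) + v2²/(n2−1)]
- noncentrality = d/SE
- power = P(|T| > t(1−α/2, df)), with T noncentral t.

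**Step 1: reproduce the printed figure (36 vs 15).** v1 = 40.96/36 = 1.138 and v2 = 28.09/15 = 1.873, so SE = 1.735, df = 31.5 and noncentrality = 5.1/1.735 = 2.94. At α = 0.05 the critical value is 2.038 and power is 81.3%. This matches the plan exactly and shows that the figure is a single unadjusted test.

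**Step 2: the thresholds under Hochberg with three endpoints.**
- MDRS-2 is judged at 0.05 if all three p-values are at or below 0.05.
- Otherwise it is judged at 0.05/2 = 0.025, if at least one other endpoint is also at or below 0.025.
- Otherwise it is judged at 0.05/3 = 0.0167.

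MDRS-2 always succeeds if its p-value is at or below 0.0167, and can never succeed above 0.05. Power at those two levels is therefore a floor and a ceiling that need no assumption about UPDRS or NMSS.

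| Patients | α = 0.05 | α = 0.025 | α = 0.0167 |
|---|---|---|---|
| 36 vs 15 | 81.3% | 71.9% | 66.0% |
| 38 vs 19 | 87.6% | 80.3% | 75.4% |
| 42 vs 21 (enrolment ceiling) | 90.7% | 84.7% | 80.4% |

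The printed 82.7% for 38 vs 19 is not reproduced by the stated inputs, which give 87.6%. It appears if the two SDs are exchanged between the arms. That is a separate matter; the 38 vs 19 figures here use the SDs as printed.

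**Step 3: where within the range (assumption-based).** The documents give no effect or SD for NMSS, no SD for MDS-UPDRS and no correlations, so these were varied. Simulated Hochberg power for MDRS-2 at 36 vs 15, with the same standardised effect on UPDRS and NMSS and correlations from 0 to 0.6:

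| Assumed effect on UPDRS and NMSS | MDRS-2 power |
|---|---|
| 0 | about 66-67% |
| 0.4 | about 66-68% |
| 0.6 | about 69-72% |
| 0.86 | about 75-77% |
| 1.2 | about 80% |
| 1.5 | about 81% |

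For scale, the MDRS-2 effect itself is 5.1/√[(6.4² + 5.3²)/2] = 5.1/5.88 = 0.87.

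**The case against.** The strongest reply is that Hochberg is not clearly the primary rule. The sentence comes at the end of a list of further analyses and says the method will be used in addition, which can be read as supplementary. The later paragraph of the same section disclaims any adjustment, and the Sample Size Calculation names MDRS-2 as the only primary outcome. On either of the last two readings, 0.05 is the right level and 81.3% is correct. This stands: the shortfall is conditional, and what is certain is the contradiction.

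Three stronger readings are tempting, and the documents do not support them.

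- **A reader might infer that power after dropout simply is 66-77%.** That takes Hochberg as settled. Also, 77% is not an upper bound: it depends on assumed effects near 0.86, and larger effects bring power to about 80-81%. Under Hochberg the loss is 0 to 15 points (81.3 − 66.0 = 15.3), depending on endpoints for which the plan gives no planning values.
- **A reader might infer that the top-up depends on power staying above 80%.** No such threshold is in the plan. Additional enrolment, up to 63, is tied to dropout being higher than anticipated, although its stated aim is to maintain power. At 42 vs 21 with no losses, even the 0.0167 test has 80.4% power.
- **A reader might infer an arithmetic error in the 81.3%.** There is none; the figure is exact for the test it describes.

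It can also be said that 51 need not be the analysed number. The primary population is the FAS with LOCF, and withdrawal-visit scores are carried forward, so some dropouts would remain in the test and the truth may lie nearer the 38 vs 19 row. That is fair as to sample size, but LOCF may also dilute the effect, and the mismatch of rules is the same in both rows.

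**Conclusion.** The concern holds as an internal contradiction with a conditional effect on power. The plan gives one primary outcome in one place and three in two others, and both applies and disclaims a multiplicity adjustment within one section. The printed 81.3% is right if MDRS-2 is tested alone, or unadjusted, at 0.05. If the three-endpoint Hochberg rule applies, it is the best case: MDRS-2 power is 66.0% to 81.3% at 36 vs 15, and 75.4% to 87.6% at 38 vs 19.

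These bounds rest on the plan's own difference and SDs and on a family of exactly three tests. The analysis section says only UPDRS, without part or ON/OFF state. If more than one UPDRS score were in the family, the floor would be lower. The figures concern a claim on MDRS-2, the one endpoint the plan powers; the chance of success on at least one endpoint can be higher.

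**What to change.** Reconcile Endpoints, Sample Size Calculation and both paragraphs of the primary efficacy analysis before unblinding.

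**Preferred.** In the primary efficacy analysis, state that MDRS-2 change at week 54 is tested first and alone at two-sided 0.05, and that UPDRS (naming the part and the ON or OFF state) and NMSS are tested by Hochberg only if MDRS-2 succeeds. Reword Endpoints to show this order. Replace the no-adjustment sentence so that it agrees; without that edit the contradiction remains. The 81.3% then stands. The cost is wording only, with no added patients or procedures. The small downside is that UPDRS and NMSS cannot be claimed if MDRS-2 fails.

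**Alternative.** If three co-equal endpoints under Hochberg are kept, correct the no-adjustment sentence, remove the sole-primary wording from the Sample Size Calculation, and restate MDRS-2 power there as 66.0% to 81.3% at 36 vs 15 and 75.4% to 87.6% at 38 vs 19.

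Deleting the Hochberg sentence would also preserve the 81.3%. It would leave three primary tests each at 0.05, with a familywise error of up to 1 − 0.95³ = 14.3% if they were independent, and the plan would have to say so.

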- The subject has any clinical AE, laboratory abnormality, intercurrent illness, or other medical condition that indicates to the PI that continued participation is not in the best interest of the subject or if it requires the subject to stop taking levodopa or other medications essential to the treatment of Parkinson's disease. Subjects experiencing AEs that are present at the end of their participation in the study should receive follow-up, as appropriate. If possible, the outcome of any AE resulting in withdrawal from the study or that was present at the end of the study will be followed until resolution or return to baseline condition, particularly if the AE was considered by the PI to be related to the study drug;
- The subject requires a concomitant medication that is prohibited in the study;
- The subject wishes to withdraw consent from the study in the absence of a medical need to withdraw, as determined by the Investigator;
- The PI concludes that it is in the best interest of the subject to discontinue study treatment;
- The subject is noncompliant; or
- If pregnancy is suspected while the subject is receiving study treatment, the study medication must immediately be withheld until the result of pregnancy testing is known. If pregnancy is confirmed, the study medication will be permanently discontinued and the subject withdrawn from the study. Reasonable attempts will be made to follow the pregnancy to conclusion in order to obtain information regarding the outcome.

The PI must complete all applicable final visit procedures (e.g., safety laboratory parameters, ECG, physical examination, vital signs [including orthostatic BP and HR]) and study documentation for subjects who withdraw from the study treatment and specify the reason for their withdrawal. Once subjects withdraw from the study, they will revert to the care of their usual physician for treatment/management of their disease as appropriate.

Subject Replacement: A subject who withdraws from the study may not reenter the study.

Rationale for Study Population: (see Background and Significance)

Visit Procedures: (see Study Schedule)

Assessments for Efficacy: The efficacy of liraglutide will be assessed by measures of the drug's effects versus placebo on PD motor and non-motor symptoms quantified on the following scales after study medication titration in active and placebo groups:

- MDS-UPDRS part I, II, III and IV changes from ON medication baseline at 28 and 54 weeks

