The final determination of protocol violations, and therefore the composition of the PP population, will be made prior to unblinding the database and will be documented separately. Analysis of all efficacy

Table 1 (from Aviles-Olmos et al., 2013⁵¹)

Changes in the score on LED, dyskinesia rating scale, Mattis DRS-2, MADRS, and PDQ39 summary index between baseline and month 14

	Baseline	6 months	12 months	Difference, baseline to 12 months	14 months	Difference, baseline to 14 months
	Mean (SD)	Mean (SD)	Mean (SD)	Mean (SD); 95% CI	Mean (SD)	Mean (SD); 95% CI
LED						
Exenatide	973 (454)	1011 (518)	997 (446)	24.3 (123.6); -37, 78	1015 (467)	42.3 (137); -22, 107
Conventional PD medication	977 (493)	1061 (613)	1121 (620)	143.7 (223.6); 49, 238	1125 (638)	148.0 (232); 50, 246
Dyskinesia rating scale, on medication						
Exenatide	2.3 (2.8)	2.5 (4.1)	3.3 (4.5)	1.0 (4.2); -1.0, 3.0	3.2 (4.0)	1.0 (3.8); -0.8, 2.7
Conventional PD medication	2.6 (2.9)	3.5 (3.9)	2.5 (2.7)	-0.04 (2.7); -1.2, 1.1	2.7 (3.5)	0.1 (4.3); -1.7, 1.9
MATTIS DRS-2						
Exenatide	140.1 (7.7)	142.4 (2.3)	142.3 (2.5)	2.2 (6.4); -0.8, 5.2	142.9 (2.0)	2.8 (6.0); -0.1, 5.6
Conventional PD medication	139.5 (4.5)	138.2 (5.1)	136.6 (6.1)	-2.8 (5.3); -0.6, -5.0	135.9 (8.5)	-3.5 (5.8); -1.1, -6.0
MADRS						
Exenatide	10.9 (5.1)	8.6 (4.2)	9.0 (4.5)	-1.9 (4.6); -4.1, 0.3	10.2 (6.7)	-0.7 (5.9); -3.5, 2.1
Conventional PD medication	11.0 (5.4)	11.3 (6.5)	11.4 (5.6)	0.5 (4.5); -1.4, 2.4	12.4 (5.6)	1.5 (4.7); -0.5, 3.4
PDQ39 summary index						
Exenatide	19.2 (13.5)	18.1 (13.4)	19.6 (13.0)	0.4 (11.4); -4.9, 5.7	21.5 (19.6)	2.3 (11.6); -3.1, 7.7
Conventional PD medication	24.5 (12.8)	25.2 (15.8)	24.0 (15.3)	-0.6 (11.2); -5.3, 4.2	23.4 (16.0)	-1.2 (9.1); -5.0, 2.7

variables will be performed on the FAS and PP population. The FAS population will serve as the primary population for the analysis of efficacy data. Analyses based on the PP population will be considered as a sensitivity analysis. Subjects will be analyzed for efficacy according to the treatment to which they were randomized.

All safety outcomes will be analyzed using the Safety population. Subjects will be analyzed for safety according to the treatment they actually received.

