The last UPDRS, NMSS, and MDRS-2 scores prior to first drug administration will be used as the baseline value in the model and to calculate change from baseline clinical scores. To calculate the change from baseline at week 54, the clinical scores at week 54 will be used. Missing values will be imputed using the last observation carried forward (LOCF) method, including clinical scores on the discontinuation visit. Baseline values will not be carried forward. This methodology will be applied to all treatment groups (liraglutide and placebo).

The assumptions of normality and homogeneity of variance will be explored using probability and residual plots. Data will be tested for normality using the Shapiro-Wilk test. If any of the assumptions are found to be violated, an appropriate transformation of the data or non-parametric test will be considered.

Sensitivity analyses of the primary efficacy endpoint will be performed on the PP population using the same methods described for the FAS population. Summaries of clinical scores, including the change from baseline, will be presented at each visit (i.e., baseline, Week 28, and Week 54). No adjustments have been made to the Type I error rate for the multiple comparisons of the primary or secondary endpoints since this is a phase II study; therefore, results should be interpreted appropriately. No statistical testing within treatment groups will be performed.

Inferential Statistics on Secondary Efficacy Parameter(s): Analyses of secondary efficacy endpoints will be conducted on the FAS and PP populations. The following secondary efficacy endpoints will be analyzed using an approach similar to that described for the primary efficacy endpoints:

- Change in PDQ-39 scores for each domain and total score between baseline and week 54.
- Change in Delis-Kaplan Executive Function System (DKEFS) between baseline and week

- Change in Geriatric Depression Scale between baseline and week 54
- Change in Parkinson's Anxiety Scale scores between baseline and week 54

The safety outcomes of this study will be the following:

- Adverse events
- Serious adverse events
- Clinical laboratory parameters
- Geriatric Depression Scale
- Vital signs
- Physical examination.
- 12-lead ECGs

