Baseline evaluation visit

After confirmation of eligibility criteria, subjects will subsequently be randomized to one of the two treatment arms. They will then undergo MDS-UPDRS OFF and ON testing and Neuropsychological testing (ON). The practically defined OFF condition will be considered an overnight withdrawal of dopaminergic medications for 12 hours while ON evaluation will be performed 1 hour (\pm 15 minutes) after the administration of the usual morning dose of dopaminergic medications. The first daily dose of 0.6 mg and/or placebo, including injection instructions, will be administered at the end of the baseline visit. The baseline visit is to be conducted within 30 days of screening.

Commence treatment: 2-week titration

The following two visits will be dedicated to medication titration, up to 1.2mg (Week 1) and 1.8 mg (Week 2), as tolerated. At every visit, study drug compliance will be reviewed. Adverse events will be assessed and concomitant medications, routine vitals, and ECG, and blood and urine tests will be collected. A phone interview will be conducted following titration to determine which dosage (1.2 mg or 1.8 mg) the patient will remain on for the duration of the study.

Follow-up visit 1 and 2

4 and 12 weeks after titration is completed, a follow-up visit will establish whether the subjects are tolerating study medications, including an assessment of adverse events, concomitant medications, routine vitals, an ECG, and blood and urine tests.

Follow-up visit 3 (6 month)

26 weeks after completing titration, subjects will undergo repeat MDS-UPDRS OFF and ON testing and

Neuropsychological testing (ON) in addition to an assessment of adverse events, concomitant medications, routine vitals, an ECG, and blood and urine tests.

Follow-up visit 4 (9 months)

36 weeks after titration is completed, a follow-up visit will establish whether the subjects are tolerating study medications, including an assessment of adverse events, concomitant medications, routine vitals, and ECG, and blood and urine tests.

End visit

52 weeks after completing titration, subjects in both treatment arms will undergo an exit visit including MDS-UPDRS OFF and ON testing and neuropsychological testing (ON) in addition to an assessment of adverse events, concomitant medications, routine vitals, an ECG, and blood and urine tests. At this stage, study treatment will be discontinued.

Post-study visit

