4 weeks after the end of the study, a phone interview will be completed to assess adverse events which were ongoing at the end visit (Week 54) and concomitant medications.

Post-study follow-up (6 month)

26 weeks after completing the active phase of the study (end visit), subjects originally assigned to both treatment arms will undergo a follow-up visit including MDS-UPDRS OFF and ON testing and neuropsychological testing (ON) in addition to an assessment of adverse events which were ongoing at the end visit (Week 54), concomitant medications, routine vitals, an ECG, and blood and urine tests. At this stage, enrolled subjects will no longer be on study treatment. However, the study team may continue to follow subjects who opt to continue liraglutide off-label.

Post-study follow up (12 month)

52 weeks after completing the active phase of the study (end visit), subjects originally assigned to both treatment arms will undergo a follow-up visit including MDS-UPDRS OFF and ON testing and neuropsychological testing (ON) in addition to an assessment of adverse events which were ongoing at the end visit (Week 54), concomitant medications, routine vitals, an ECG, and blood and urine tests. At this stage, enrolled subjects will no longer be on study treatment. However, the study team may continue to follow subjects who opt to continue liraglutide off-label.

STUDY DRUGS AND MATERIALS:

Study Medications: Liraglutide 6 mg/ml (Novo Nordisk A/S) will be self-administered subcutaneously once daily at a maximum dose of 1.8 mg after a 2 week titration schedule. Placebo will be administered according to the same schedule (Table 2). At baseline, subjects will be dispensed drug pens preset to deliver 0.6 mg of either liraglutide or vehicle per daily dose. At week 1 visit, after being assessed for tolerability by the investigator, subjects will be titrated to 1.2 mg of either liraglutide or vehicle per daily dose. The same procedure will be repeated at week 2, when subjects will be titrated to 1.8 mg of either liraglutide or vehicle per daily dose, as tolerated. A subject that cannot tolerate at least a 1.2 mg dose will be excluded from the study. Subjects that cannot tolerate the 1.8 mg dose, will be offered to continue at the 1.2 mg dose. The project will include a washout period at study end.

Table 2

Week	Titration Schedule	
	Drug Group	Placebo Group
	Liraglutide Dose	Vehicle Dose
Baseline	0.6 mg	0.6 mg
Week 1	1.2 mg	1.2 mg

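### Patients who stop early either fall out of the primary analysis set or enter it with a near-baseline score, which puts the primary comparison at risk of bias

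*Combined protocol and SAP*

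**What the plan says.** Under Statistical Methods, the FAS is "all randomized subjects who receive at least one dose of study drug and have a baseline and at least one post-baseline efficacy score", followed by a parenthesis naming MDRS-2 and MDS-UPDRS. "The FAS population will serve as the primary population for the analysis of efficacy data". The only other efficacy set is the per-protocol population, itself a subset of the FAS: "Analyses based on the PP population will be considered as a sensitivity analysis".

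Efficacy scores are scarce in time. Under Inferential Statistics on Primary Efficacy Parameter(s), score summaries "will be presented at each visit (i.e., baseline, Week 28, and Week 54"). The Study Schedule and the Schedule of events agree that no efficacy scale is due between baseline and Week 28. Missing values are filled by last observation carried forward (LOCF), which may use scores from a discontinuation visit, but "Baseline values will not be carried forward".

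Several rules take patients out before Week 28. Under Study Medications, "A subject that cannot tolerate at least a 1.2 mg dose will be excluded from the study". Under Subject Compliance, a second lapse requires termination, and compliance is reviewed at Weeks 1, 2, 6 and 14.

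Withdrawal Criteria asks for a full evaluation when a subject decides to stop. It then says of those who withdraw from treatment: "The PI must complete all applicable final visit procedures (e.g., safety laboratory parameters, ECG, physical examination, vital signs" and so on. They receive one telephone call a month later and return to their usual physician.

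**The concern.** A requirement for one post-baseline score does little harm when the first score comes soon after the first dose. Here it comes half a year later, and intolerance of study drug shows itself in the first three weeks. Whether an early leaver has any efficacy score depends on a discontinuation visit whose efficacy content the plan never spells out.

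Both possible outcomes are poor:

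- **No scales done.** The patient is outside the primary set and outside its only sensitivity set, so no planned efficacy analysis includes that patient.
- **Scales done in Weeks 1 to 3.** LOCF treats that score as the Week 54 result, so a year of possible change is recorded as almost none.

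If such losses differ between arms, the primary comparison is no longer the one that randomisation protects. Precautions/Over-dosage expects nausea in 5-40% and diarrhea in 17% on liraglutide, so greater early loss on drug is plausible.

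**Working it through.** **Inputs from the plan.** Sample Size Calculation: 38 drug and 19 placebo patients, difference 5.1 on MDRS-2, SD 6.4 (drug) and 5.3 (placebo), two-sided alpha 0.05, unequal-variance t-test. Table 1: the comparator's MDRS-2 change over 12 months is -2.8.

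**The plan's own figures.** The standard error is sqrt(6.4²/38 + 5.3²/19) = sqrt(1.078 + 1.478) = 1.60. Power from the noncentral t is 87.6%, not the stated 82.7%; the latter appears if the two SDs are swapped. The stated 81.3% at 36 and 15 patients reproduces with the SDs as written. That discrepancy is a separate matter and does not decide this point.

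**Branch 1: the early leaver is dropped.** Let p_D and p_P be the shares dropped in each arm, and g the number of points by which those dropped would have done worse than those retained, taken as equal in both arms. Then

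shift = g × (p_D − p_P).

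The plan gives no early-loss rate. The following are assumptions: 6 to 8 of 38 on drug (15.8% to 21.1%), 1 of 19 on placebo (5.3%), g from 2 to 5.

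- Low: 2 × (6/38 − 1/19) = 2 × 0.105 = 0.21 points, 4% of 5.1.
- High: 5 × (8/38 − 1/19) = 5 × 0.158 = 0.79 points, 15% of 5.1.

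These are 0.13 to 0.49 standard errors (0.21/1.60 and 0.79/1.60). With no true effect and the planned SDs, the two-sided type I error is 5.2% (32 v 18 retained, shift 0.21) to 7.4% (30 v 18, shift 0.79). The shift favours the drug under these assumptions.

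If the same share with the same prognosis leaves each arm, for example 6 of 38 and 3 of 19, the shift is 5 × (0.158 − 0.158) = 0.

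**Branch 2: a Week 1-3 score is carried forward.** Suppose leavers would have changed by -2.8, like the comparator in Table 1, but are recorded near zero. With the same loss rates:

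- 2.8 × 0.105 = 0.29 points.
- 2.8 × 0.158 = 0.44 points.

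The difference is again overstated, though every leaver has a score.

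**Power.** Nominal power with 5.1 points is 84.0% at 32 and 18, and 82.9% at 30 and 18. The issue is bias, not sample size. Enrolling up to 63 patients restores numbers but not the missing outcomes.

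**Would a longitudinal model suffice?** A model with a common baseline mean assumes that a baseline-only patient would have followed the retained patients of the same arm. That patient adds almost nothing to the treatment contrast. In a simulation with no drug effect, with 8 of 38 and 1 of 19 baseline-only patients 5 points worse, the complete-case estimate was 0.02, the constrained model gave 0.02, and the all-randomised difference was -0.77. The model does not recover the gap.

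**The case against.** The strongest reply is that the plan already covers early leavers. Withdrawal Criteria calls for a full final evaluation, the list of final procedures is only a set of examples, the End visit includes MDS-UPDRS and neuropsychological testing, and the LOCF rule mentions discontinuation-visit scores. A patient assessed that way stays in the FAS, and the Branch 1 shift is zero.

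This stands in part. The intention is visible, but the data are not secured. The full-evaluation sentence concerns a subject who decides to stop, not clearly one removed under the tolerability rule. Every named example is a safety item. There is no early-termination column, and nothing arranges the overnight medication withdrawal that the OFF assessment needs at an unplanned exit. Where the visit does work, Branch 2 applies.

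A reader might infer that intolerant patients are removed from the drug arm only, so that drug-tolerant patients are compared with all placebo patients and the result is biased towards the drug. The documents do not support that:

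- The FAS, tolerability and LOCF rules apply to both arms.
- The side-effect figures describe mild-to-moderate events in type 2 diabetes, not failure to tolerate the minimum dose.
- The one arm-specific loss scenario, 36 and 15 remaining, loses 2 of 38 on drug and 4 of 19 on placebo. With g of 2 to 5, that gives 2 × (0.053 − 0.211) = -0.32 to 5 × (0.053 − 0.211) = -0.79, the opposite direction.
- Neither the sign nor the size of the leavers' deficit is given. If it is only lost drug benefit, it vanishes when the drug has no effect.

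Nor does the expected 43 completers (Assessments for Safety) supply an early-loss rate. 43/57 is 75.4%, which conflicts with the stated figure of over 80%. It also covers both arms over the whole treatment period.

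Finally, disposition and the numbers in each population will be reported, so exclusions would be visible. Visibility does not supply the missing outcomes.

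**Conclusion.** The point holds as a risk of bias, not as demonstrated bias. As written, an early leaver is either left out of every efficacy analysis or represented by a score taken about a year too soon, and no Week 28 or Week 54 outcome is sought.

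Under the illustrative losses, either branch moves the MDRS-2 difference by a few tenths of a point, and by at most about 0.8 of the planned 5.1. That would not by itself create or erase an effect of the planned size, but it matters for a smaller effect or a borderline result. The size rests on assumed loss rates and an assumed deficit. The direction depends on which arm loses more, and the shift is zero if losses and prognosis are balanced.

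The parenthesis after the FAS definition is also unclear. It can be read as requiring both scales, so that a missing MDS-UPDRS removes a patient from the MDRS-2 analysis, or as listing the scores that count. NMSS, also a primary scale, is not mentioned there.

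**What to change.** 1. Separate stopping study drug from leaving the study. Ask every dosed patient to attend the Week 28 and Week 54 efficacy visits, whatever the reason for stopping. Reconcile Withdrawal Criteria, Study Medications and the LOCF paragraph on this.
2. Name MDRS-2, MDS-UPDRS and NMSS as required at any discontinuation visit, and add an early-termination column to the Schedule of events.
3. Make the primary set all randomised and dosed patients, analysed as randomised. Use observed off-drug scores in place of LOCF where they exist. Add a sensitivity analysis that assumes worse outcomes, over a stated range, for patients with no post-baseline score.
4. Apply the score requirement separately to each scale.

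A longitudinal model may be used, but not in place of items 1 to 3.

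The cost is some SAP and protocol wording, a few extra visits by patients who have stopped drug, and slight dilution of the estimate by their off-drug scores. No dose or treatment rule needs to change.
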